1.0 BACKGROUND AND RATIONALE

1.1 Disease Background

Leiomyomata are the most common tumors of the uterus. Though the majority of women with fibroids are asymptomatic, a significant portion suffer symptoms including abnormal bleeding, pain, pressure and abdominal distention (1). Submucosal and large intramural fibroids have also been shown to impair fertility. Many women seek treatment for fibroids but desire to retain their uterus, whether to preserve future fertility or for other personal reasons. Myomectomy is a curative treatment that allows for uterine preservation but can come at the risk of substantial intraoperative blood loss.

Studies have assessed the utility of GnRH, vasopressin, peri-cervical tourniquet, misoprostol and oxytocin, among others, in reducing intraoperative blood loss (2). Findings from small randomized trials demonstrate significantly lower intraoperative blood loss among women who receive preoperative misoprostol compared to those who receive placebo (4, 6, 7). Other research fails to demonstrate a difference in blood loss following preoperative misoprostol (8) and cites methodologic flaws with existing studies (5). Additionally, no randomized controlled trial has been done in a U.S. population. A double-blinded, randomized, placebo-controlled trial at a tertiary care center in a major U.S. city is an ideal setting for evaluation of this research question.

The aim of this study is to assess the impact of preoperative buccal misoprostol on intraoperative blood loss and clinical outcomes related to blood loss (blood transfusion, protracted hospital stay). Defining the relationship between misoprostol and blood loss during myomectomy would provide insight into the mechanism of uterine contraction and hemostasis and inform optimal preoperative clinical management of patients undergoing this common and potentially morbid procedure.

1.2 Study Agent(s)/Devices Background and Associated Known Toxicities

Misoprostol is an analogue of prostaglandin E1 initially developed for treatment of NSAID induced peptic ulcers, which is currently used in a variety of contexts in the field of obstetrics and gynecology including in the FDA approved regimen for medical abortion, cervical ripening, and treatment of postpartum hemorrhage. In non-pregnant women, misoprostol has been widely described for use in cervical preparation prior to hysteroscopy, intrauterine device insertion, and endometrial biopsy.

Multiple routes of administration have been studied including oral, sublingual or buccal, rectal and vaginal administration with peak plasma concentrations less than 30 minutes after administration via the oral or sublingual route. Systemic bioavailability of sublingual misoprostol is significantly greater than with orally or vaginally administered misoprostol however overall plasma concentrations persist for at least 6 hours at higher concentrations when administered vaginally. Potent uterotonic activity is noted as a result of increased intracellular calcium activating myosin light-chain kinase.

Adverse effects of misoprostol vary and include abnormal vaginal bleeding, lower abdominal pain and cramping, fever or shivering, nausea, vomiting and diarrhea with more uterine cramping and vaginal bleeding associated with vaginal administration (3).

Prior studies evaluating misoprostol effect on intraoperative blood loss at time of either an abdominal and laparoscopic myomectomy have used a single dose of 400mcg misoprostol administered vaginally or rectally pre-procedure and have found a significant decrease in blood loss. 400mcg is the standard dose used for the majority of gynecologic applications and appears to be well tolerated (4-9). There are no additional risks to study participants adding laparoscopic surgery to this study.

1.3 Other Agents/Devices

Placebo will be 100mg vitamin B6 (pyridoxine) tablets (see Section 8.2).

1.4 Rationale

Abdominal myomectomy is a common procedure that comes with risks of significant morbidity, including intraoperative blood loss at time of abdominal myomectomy as well as numerous postoperative complications including an up to 20% requirement for transfusion and 2% reported conversion to hysterectomy. The significant morbidity associated with this procedure has led to studies evaluating multiple interventions to reducing bleeding during myomectomy. A systematic review of the interventions to reduce blood loss at time of myomectomy found significant reductions in blood loss with use of vaginal misoprostol however included only one randomized controlled trial (2). Since this time, other studies have been done that reproduce these findings (6, 7), though sample size in these trials is small and results are inconsistent (8). This study would augment existing data by employing a larger sample size and double-blinded design in a U.S. population. This study would also assess the impact of a route of misoprostol administration that is less invasive for patients (buccal instead of vaginal or rectal) but offers a similar pharmacokinetic profile. Outcomes assessed include estimated blood loss, need for transfusion, prolonged hospitalization, change in postoperative hemoglobin level from preoperative baseline.

1.5 Correlative Studies n/a**2.0 STUDY OBJECTIVES****2.1 Primary Objectives**

2.1.1 To determine the effect of 400mcg buccal misoprostol at least one hour pre-procedure on intraoperative blood loss at time of either an abdominal or laparoscopic myomectomy.

2.2 Secondary Objectives

2.2.1 To determine the effect of 400mcg buccal misoprostol at least one hour pre-procedure on the need for blood transfusion during or in post-operative course for either an abdominal or laparoscopic myomectomy

2.2.2 To determine the effect of 400mcg buccal misoprostol at least one hour pre-procedure on post-operative fever after either an abdominal or laparoscopic myomectomy.

2.2.3 To determine the incidence of adverse effects, if any, of 400mcg buccal misoprostol at least one hour prior to either an abdominal or laparoscopic myomectomy.

2.3 Exploratory Objectives n/a**2.4 Endpoints**

Estimated blood loss as determined by anesthesia and surgeon at time of abdominal or laparoscopic myomectomy, difference between post-operative and pre-operative hemoglobin, post-operative temperature, and overall length of hospital admission.

3.0 PATIENT ELIGIBILITY

Subjects must meet all of the inclusion and exclusion criteria to be registered to the study. Study treatment may not begin until a subject is registered.

3.1 Inclusion Criteria

- 3.1.1 Patients presenting for either an abdominal and myomectomy with documented uterine fibroids on pelvic imaging (pelvic ultrasound or MRI) within in last 12 months
- 3.1.2 Age \geq 18 years and \leq 50 years.
- 3.1.3 Pre-operative hemoglobin >8 g/dl.
- 3.1.4 Willing to have buccal administration of misoprostol or a placebo at least one hour pre-procedure.
- 3.1.5 Ability to understand and the willingness to sign a written informed consent.
- 3.1.6 Admissible medical/surgical history.
 - a. Can be previously treated with Depo-Lupron, Depo-Provera, or Oral Contraceptive pills
 - b. Intraoperative use of vasopressin and uterine tourniquet is permissible
 - c. Can have had prior Cesarean delivery

3.2 Exclusion Criteria

- 3.2.1 Pregnancy. All patients will be required to have a negative urine pregnancy test prior to enrollment.
- 3.2.2. Patients who have had a prior abdominal myomectomy.
- 3.2.3 Post-menopausal women.
- 3.2.4 Patients with known bleeding/clotting disorders.
- 3.2.5 Patients with a history of gynecologic malignancy.
- 3.2.6 History of allergic reactions attributed to compounds of similar chemical or biologic composition to misoprostol.
- 3.2.7 Any cases converted to abdominal hysterectomy or other additional elective surgical procedures performed at time of abdominal or laparoscopic myomectomy will be excluded from data analysis.
- 3.2.8 Uncontrolled intercurrent illness including, but not limited to, ongoing or active infection, symptomatic congestive heart failure, unstable angina pectoris, cardiac arrhythmia, or psychiatric illness/social situations that would limit compliance with study requirements.

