5.1.2 Medical history

Complete medical, surgical, gynecologic and obstetrical history, medications, allergies, social and family history including and history of prior myomectomy and personal or family history of blood dyscrasias,

coagulopathy and bleeding disorders.

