5.1.4 Review subject eligibility criteria

Refer to section 3.0.

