7.1.1 Contraindications

Pregnancy, history of allergy to prostaglandins or Vitamin B6.

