8.0 DRUG/DEVICE INFORMATION

8.1 Agent/Device: Misoprostol

- Other names for the drug(s)/device: Cytotec
- Classification - type of agent/device: medication, synthetic Prostaglandin E1 analogue
- Mode of action: Production of uterine contractions
- Storage and stability: Store at or below 25°C (77°F), in a dry area.

- Protocol dose: 400mcg
- Preparation: Tablet
- Route of administration for this study: Buccally, 200mcg on each side
- Incompatibilities: Pregnancy, history of adverse reaction to prostaglandins
- Availability: Commercially available
- Side effects: A brief summary of the adverse events most likely to occur in this study and associated with this agent should be inserted here. Refer the reader to the agent's package insert or Section 7.1 above for a comprehensive list of adverse events.
- Nursing implications: Ensure patient has a negative pregnancy test and confirm list of allergies prior to providing the medication. Day of surgery urine pregnancy testing and verbal confirmation of a patient's allergies are both standard of care practices for reproductive age women undergoing surgery.

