8.2 Agent/Device: Vitamin B6

- Other names for the drug(s)/device: Pyroxidine
- Classification - type of agent/device: medication, synthetic vitamin
- Mode of action: Vitamin B6 in coenzyme forms performs a wide variety of functions in the body and is extremely versatile, with involvement in more than 100 enzyme reactions, mostly concerned with protein metabolism (12).
- Storage and stability: Store at or below 25°C (77°F), in a dry area.
- Protocol dose: 100mg
- Preparation: Tablet
- Route of administration for this study: Buccally, 50 mg on each side
- Incompatibilities: none
- Availability: Commercially available
- Side effects: none
- Nursing implications: none

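### Vitamin B6 allergy is listed as a contraindication but is not an exclusion, so a woman with that allergy can be randomised to the B6 placebo

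*Combined protocol and SAP*

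**What the plan says.** The comparator is an active substance: Sections 1.3 and 4.1 define the placebo as 100 mg of vitamin B6, given buccally.

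- **Contraindications (7.1.1):** "Pregnancy, history of allergy to prostaglandins or Vitamin B6".
- **Allergy exclusion (3.2.6):** "History of allergic reactions attributed to compounds of similar chemical or biologic composition to misoprostol". This is the only allergy item in 3.1 or 3.2.
- **Entry rule (3.0):** "Subjects must meet all of the inclusion and exclusion criteria to be registered to the study". The eligibility review in 5.1.4 adds no further list; it says "Refer to section 3.0".
- **Placebo drug information (8.2):** "Incompatibilities: none" and "Nursing implications: none".
- **Misoprostol drug information (8.1):** pregnancy and prior adverse reaction to prostaglandins are given as incompatibilities, and the nursing instruction is "Ensure patient has a negative pregnancy test and confirm list of allergies prior to providing the medication".
- **Screening history (5.1.2):** "Complete medical, surgical, gynecologic and obstetrical history, medications, allergies, social and family history", so allergies are recorded for every woman.

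**The concern.** In a double-blind trial each woman may receive either tablet, so a contraindication to either one should be screened out before randomisation. The protocol does this for pregnancy and for prostaglandin-type allergy. It does not do it for vitamin B6 allergy, although 7.1.1 puts that allergy on the same line as the other two.

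Two things could follow. If the later checks fail and the woman is in the placebo arm, she is exposed to a substance the protocol says she should not have. If the pre-dose check stops her, she is a randomised woman who was not treated. Because staff are blinded, they would have to stop her whichever arm she was in. That is an avoidable loss, and Section 10.2 shows that such losses count in this trial: participants who did not get the study drug were among the 9 for whom the sample was raised from 50 to 70.

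**Working it through.** This is mainly a check of one section against another; no figure in the plan turns on it.

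**Step 1. Are the contraindications carried into Section 3?**

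| Contraindication in 7.1.1 | Exclusion in Section 3 | Drug information in Section 8 |
|---|---|---|
| Pregnancy | 3.2.1 | Listed in 8.1 |
| Prostaglandin allergy | 3.2.6 | Listed in 8.1 |
| Vitamin B6 allergy | None | 8.2 says there are no incompatibilities |

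Of the two allergy contraindications, one is carried over.

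**Step 2. Could another item cover vitamin B6?** The protocol classes misoprostol as a synthetic prostaglandin E1 analogue (8.1) and vitamin B6 as a synthetic vitamin (8.2), so 3.2.6 cannot fairly be stretched to B6. Item 3.2.8 concerns uncontrolled intercurrent illness. Item 3.1.4 asks only for willingness to take either tablet. The exclusions restated in 10.1 contain no allergy item, and neither do those marked in the variable table. B6 allergy is named once in the protocol, in 7.1.1.

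**Step 3. What follows at entry?** Registration depends on Section 3 (3.0), and 5.1.4 sends the reviewer back to Section 3. A woman with a known B6 allergy who meets everything else is therefore eligible.

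**Step 4. Size.** The Study Summary gives 70 subjects, 35 per arm.

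- Chance of allocation to B6: 35/70 = 0.50. This is allocation, not receipt. The chance of receipt is lower, by an amount the documents do not allow us to estimate.
- One woman lost: 1/35 = 2.9% of an arm, or 1/70 = 1.4% of the trial.
- Power for a 1 SD difference, two-sided t-test at 0.05, with noncentrality √(n₁n₂/(n₁+n₂)):
  - 35 v 35: √(1225/70) = 4.18 on 68 df, power 98.5%.
  - 35 v 34: √(1190/69) = 4.15 on 67 df, power 98.4%.

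The Study Summary attaches 90% power to 35 per arm for the same difference, which this calculation does not reproduce. That is a separate matter. The figures here serve only to show that one loss makes no practical difference.

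**The case against.** The strongest reply is that the woman would almost certainly not be dosed. Allergies are part of the screening history (5.1.2). Section 8.1 has the allergy list confirmed before the tablet is given, and adds that verbal confirmation of allergies on the day of surgery is standard care. Blinded nurses could not apply 8.1 to one arm and 8.2 to the other, so in practice the check covers both. An investigator who sees a recorded B6 allergy can read 7.1.1 and decline to enrol her, or withdraw her for safety under 5.4. A woman who knows of the allergy and is told what the placebo contains would be expected to refuse; the consent pages are not available, so whether she is told cannot be checked. Section 6.1 describes a single dose of pyridoxine as having no known side effects. Finally, an undosed woman who still has surgery has a recorded blood loss, 4.7 keeps removed patients in follow-up, and 4.8 allows replacement.

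Most of this stands, and it is why the point is minor. It makes exposure unlikely and shows that an undosed woman need not be lost to analysis. It does not close the gap. None of these safeguards is an eligibility criterion, the day-of-surgery check comes after registration, and the statement about side effects does not rule out allergy. Section 10.2 suggests the team does treat undosed women as losses. And the conflict between 7.1.1 and 8.2 remains whatever the practice is: if the sponsor thinks B6 allergy irrelevant, 7.1.1 is the section that is wrong.

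**Conclusion.** The concern holds, as a minor fault. The eligibility rule and the placebo entry both disagree with the protocol's own contraindication, and a woman with a known B6 allergy can be randomised as the text stands. The claim is about eligibility and allocation; it is not that she would be dosed. The stop comes after randomisation unless someone applies 7.1.1 before registration.

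The conclusion rests on the wording of the sections compared above and assumes no rate of B6 allergy, since the documents give none. The number of women affected is probably very small or zero. Power, error rate and analysis are in practice unaffected. The reason to act is patient safety and a consistent entry rule.

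**What to change.** 1. Extend 3.2.6 so that it reads: "History of allergic reactions attributed to compounds of similar chemical or biologic composition to misoprostol", or to vitamin B6 (pyridoxine).
2. In 8.2, replace the incompatibilities entry with history of allergy to vitamin B6.
3. In 8.2, replace the nursing entry with the same pre-dose allergy check as in 8.1.

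The prostaglandin wording in 8.1 can stay as it is.

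The cost is one phrase and two entries. Allergies are already recorded under 5.1.2, so no new question or test is needed, and the sample size and analysis do not change.

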4.0 TREATMENT PLAN**4.1 Treatment Dosage and Administration**

- 4.1.1 400mcg misoprostol or 100mg vitamin B6 placebo administered buccally at least one hour prior to procedure.

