4.8 Patient Replacement

If a patient is removed from the study, an additional patient may be enrolled and randomized to replace them.

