5.4 Removal of Subjects from Study

Patients can be taken off the study treatment and/or study at any time at their own request, or they may be withdrawn at the discretion of the investigator for safety, behavioral or administrative reasons. The reason(s) for discontinuation will be documented and may include:

- 5.5.1** Patient voluntarily withdraws from treatment (follow-up permitted);
- 5.5.2** Patient withdraws consent (termination of treatment and follow-up);
- 5.5.3** Patient is unable to comply with protocol requirements;
- 5.5.4** Patient experiences toxicity that makes continuation in the protocol unsafe;
- 5.5.5** Treating physician judges continuation on the study would not be in the patient's best interest;
- 5.5.6** Patient becomes pregnant (pregnancy to be reported along same timelines as a serious adverse event);
- 5.5.7** Lost to follow-up. If a research subject decides against undergoing abdominal or laparoscopic myomectomy and/or surgical case is cancelled after receiving misoprostol or placebo, the

subject may be considered lost to follow-up.

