10.0 STATISTICAL CONSIDERATIONS

10.1 Study Design/Study Endpoints

This is a double blinded randomized, controlled trial of women undergoing either an abdominal and laparoscopic myomectomy at a single university-affiliated tertiary care center. Women ages 18-50 years of age with clinically documented, sonographic evidence of uterine fibroids being scheduled for abdominal myomectomy were eligible for inclusion. Eligible participants will be randomized to receive preoperative 400cg buccal misoprostol or placebo on the basis of total fibroid volume, location (intramural or subserosal) and parity. Stratification by fibroid volume (or fibroid size) will be performed prior to randomization. Fibroid volume is defined as the cumulative volume of intramural and subserosal fibroids as measured on preoperative magnetic resonance imaging (MRI), or in the instance of patient contraindication to MRI, transvaginal ultrasound (TVUS). The data collection sheet (addendum) and chart of study variables below include definition of this variable and allow for ease of recording and tracking of this variable in our study database. Women with a history of gynecologic malignancy, critical anemia or blood dyscrasias and those with a history of prior myomectomies will be excluded.

List of Study Variables to be Collected:

Outcomes	Type	Definition
Estimated blood loss	Continuous	Intraoperative blood loss as estimated by intraoperative anesthesiologists and surgeons.
% drop in Hgb	Continuous	Ratio of the drop in hemoglobin over the starting hemoglobin ($Hg_{post-op} - Hg_{pre-op}$)/ Hg_{pre-op}
Duration of hospital stay (days)	Continuous	Number of days inpatient following abdominal myomectomy.
Duration of procedure (minutes)	Continuous	Number of days inpatient following abdominal myomectomy.
Post-op fever	Dichotomous	If patient has one Temperature >101.4 or two temperatures >100.4 , then yes. If not then no.
Adverse reaction to misoprostol	Dichotomous	If patient experiences vaginal bleeding, vomiting or diarrhea then yes. If not then no.

Exposures	Type	Definition
Pre-op Misoprostol	Dichotomous	If women randomized to receive misoprostol, then yes. If women randomized to placebo, then no.

Covariates	Type	Definition
Woman's Age	Continuous	Female age in years at time of abdominal myomectomy
Volume of fibroids (pre-op)	Continuous	Cumulative volume of intramural and subserosal fibroids based on preoperative imaging Will be used for stratification and randomization.

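### Section 3.2.7 removes women converted to hysterectomy from the analysis after randomisation and dosing, and no as-randomised blood-loss analysis is planned beside it

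*Combined protocol and SAP*

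**What the plan says.** Section 3.2.7, in the list of exclusion criteria, states that "cases converted to abdominal hysterectomy or other additional elective surgical procedures performed at time of abdominal or laparoscopic myomectomy will be excluded from data analysis". Section 3.0 says of that list: "Subjects must meet all of the inclusion and exclusion criteria to be registered to the study". Under 4.1.1 the study drug is "administered buccally at least one hour prior to procedure", so anything that happens during surgery comes after allocation and dosing.

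The primary objective (2.1.1) is the effect of misoprostol "on intraoperative blood loss at time of either an abdominal or laparoscopic myomectomy". Section 10.1 defines estimated blood loss (EBL) as "Intraoperative blood loss as estimated by intraoperative anesthesiologists and surgeons". Section 1.4 describes the morbidity of abdominal myomectomy. Besides intraoperative blood loss it cites "up to 20% requirement for transfusion and 2% reported conversion to hysterectomy", and it says this morbidity prompted studies of ways to reduce bleeding. It does not say why conversions occur and gives no rate for laparoscopic cases.

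Section 10.3 plans linear regression for blood loss and t tests and Fisher's exact tests elsewhere. It names no analysis population and no sensitivity analysis. Section 10.1 codes exposure by randomised arm, which settles how women are grouped but not who is included. Section 4.2 keeps treated women evaluable for toxicity only.

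**The concern.** The rule conditions the analysis set on an event that follows randomisation and may depend on the primary outcome. If heavy bleeding leads to conversion and misoprostol reduces bleeding, more of the heaviest bleeders are dropped from the placebo arm than from the active arm. The remaining placebo women then look better than the randomised placebo group, and the estimated benefit shrinks. With about 35 women per arm, one or two extreme values can move a mean. What is at stake is the size of the reported effect, and a reader's ability to see how far it depends on the exclusion.

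**Working it through.** **The plan's own figures.** The plan gives no count of expected exclusions and no estimate of their effect. Its planning effect is 1 SD with 90% power and 25 per arm (10.2). Check: 2 × (1.960 + 1.282)² / 1² = 21.0, so 22 per arm by the normal approximation and 23 by the two-sided t test; 25 is consistent. At 35 per arm the t-test power for 1 SD is 98.5%.

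**How many women.** Inputs: 70 women (Study Summary, 10.2) and 2% conversion (1.4), assumed to apply in both arms and to both surgical routes.
- Expected conversions: 0.02 × 70 = 1.4.
- At least one: 1 − 0.98^70 = 0.757.
- Arms differing by two or more, from two independent Bin(35, 0.02): 0.177.

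**How much bias, if conversion follows bleeding.** The documents give no EBL distribution, so these are assumptions: lognormal EBL, placebo median 300 mL, log-SD σ of 0.6, 0.8 or 1.0, and active median lower by 30%, 50% or 70%. Every conversion is bleeding-driven under one rule in both arms: a fraction q of women above a cutoff c convert, with q = 0.2 (loose) or q = 1 (hard). The cutoff is set so that placebo conversion is 2%.

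For an arm with median m, let z = (ln c − ln m)/σ. Then
- mean, all women: m·exp(σ²/2)
- mean after exclusion: m·exp(σ²/2) × [1 − q·Φ(σ − z)] / [1 − q·Φ(−z)]

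Worked case: σ = 0.8, 30% reduction, hard cutoff c = 1,551 mL.
- Placebo, z = 2.054: 300 × exp(0.32) = 413.1 mL; after exclusion 413.1 × (1 − 0.105)/0.98 = 377.3 mL.
- Active, m = 210, z = 2.50: 289.2 mL; after exclusion 289.2 × (1 − 0.0446)/0.9938 = 278.0 mL.
- The difference moves from −123.9 to −99.3 mL, a shift of 24.6 mL; 24.6/123.9 = 19.9% understatement.

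| log-SD | Reduction | All women (mL) | Loose (mL) | Hard (mL) | Understated, loose/hard |
|---|---|---|---|---|---|
| 0.6 | 30% | −107.7 | −100.5 | −92.4 | 6.7% / 14.2% |
| 0.6 | 50% (d = 0.96) | −179.6 | −169.7 | −160.9 | 5.5% / 10.4% |
| 0.6 | 70% | −251.4 | −240.7 | −232.0 | 4.3% / 7.7% |
| 0.8 | 30% | −123.9 | −113.7 | −99.3 | 8.3% / 19.9% |
| 0.8 | 70% (d = 1.00) | −289.2 | −271.6 | −253.7 | 6.1% / 12.3% |
| 1.0 | 30% | −148.4 | −134.0 | −109.7 | 9.7% / 26.1% |
| 1.0 | 70% | −346.2 | −318.9 | −284.3 | 7.9% / 17.9% |

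The full grid, which also has 50% reductions at log-SD 0.8 and 1.0, stays within 4.3-26.1%. Values above 20% occur only with the hard cutoff at log-SD 1.0. The shift is 7-62 mL, or 0.11-0.54 of a standard error. Expected exclusions are 0.7 in placebo and 0-0.35 in active.

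**Power and type I error.** In 40,000 simulated trials per case (35 per arm, unadjusted t test, 30% reduction), the largest change in power was 0.618 to 0.600. In two hard-cutoff cases the exclusion did not lower power (0.355 to 0.356; 0.219 to 0.231). With no true effect, rejection was 0.041-0.049 with all women and 0.043-0.050 after exclusion.

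**Bias against variance.** In the worked case the standard error is 81 mL with all women and 62 mL after exclusion. The root-mean-square error (RMSE) after exclusion is √(24.6² + 62²) ≈ 67 mL, against 81 mL with everyone kept. RMSE around the all-women difference was lower with the exclusion in all 18 combinations, from a near-tie (67.8 against 69.1 mL; log-SD 0.8, 70%, loose) to 98.3 against 133.8 mL (log-SD 1.0, 30%, hard).

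**The case against.** The strongest reply is that the rule is pre-stated, applies to both arms of a double-blind trial, and touches about one woman in 70. Any expected bias is towards no effect, and on RMSE the exclusion does slightly better in these models. All of that stands and limits the weight of the point. It does not justify leaving out the as-randomised result: the lower RMSE comes from trimming the outcome's upper tail, and the price is an estimate that is too small on average if conversion follows bleeding.

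Second, the exclusion has a defensible purpose. EBL in a converted case includes hysterectomy bleeding, while objective 2.1.1 concerns blood loss at myomectomy. This also stands. The protocol does not give that reason, however, and it plans only the one analysis.

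Third, the wording could be read as aimed at elective additions rather than at conversions forced by bleeding. The natural reading covers every conversion. Additional elective procedures are less likely to be bleeding-driven, and excluding those planned before randomisation is reasonable.

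A reader might infer that conversions are caused by bleeding. Section 1.4 lists the two together but states no cause, so the link is plausible, not shown. A reader might also treat the placement of 3.2.7 among eligibility criteria as a fault in itself. That is editorial, since the criterion says openly that it concerns the analysis.

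**Conclusion.** The point holds as a modest, conditional bias created by a stated rule that nothing in sections 10.1 to 10.3 offsets. If all conversions are bleeding-driven, misoprostol works and placebo conversion is 2%, the mean EBL benefit is understated by about 4-26% (7-62 mL, 0.1-0.5 SE). The range rests on assumed lognormal distributions. The expected bias is zero if conversion is unrelated to bleeding, or if the drug has no effect and one conversion rule applies in both arms. The actual share of bleeding-driven conversions is unknown, and the 2% comes from abdominal myomectomy only.

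The stronger reading, that the exclusion could manufacture a benefit or invalidates the trial, is not supported: the expected direction is towards no effect, and power and false-positive rate barely change. Chance imbalance in a handful of conversions could still move a single trial's estimate either way.

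Nor do the documents show that other women are wrongly dropped from the EBL analysis. How to treat women without a POD 1 value or undosed (10.2), women whose "surgical case is cancelled after receiving misoprostol or placebo" (5.5.7), and women replaced under 4.8 is unclear. Those are separate clarifications, not evidence of bias.

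**What to change.** 1. Reword 3.2.7 so that it excludes only additional elective procedures planned before randomisation.
2. In 10.3, define the primary EBL analysis by randomised arm in all randomised women whose surgery was begun, including converted cases and unplanned added procedures, using recorded intraoperative EBL.
3. Report the analysis with the current 3.2.7 exclusion beside it as a sensitivity analysis.
4. Report conversions and all other exclusions by arm and reason.

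If the sponsor prefers to keep the 3.2.7 set as primary because 2.1.1 concerns blood loss at myomectomy, it should say so, and the as-randomised analysis must still be pre-specified and reported beside it.

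The cost is protocol wording; EBL is already recorded in theatre, so no new data are needed. The real downside is that the as-randomised estimate then covers the whole operation, hysterectomy bleeding included, and a few high values widen the interval, as in the 81 against 62 mL standard errors above. The required sample size does not change.
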